12.2. Appendix 2: Pharmacogenetic research

Pharmacogenetics – Background

Pharmacogenetics (PGx) is the study of variability in drug response due to hereditary factors in populations. There is increasing evidence that an individual's genetic background (i.e., genotype) may impact the pharmacokinetics (absorption, distribution, metabolism, elimination), pharmacodynamics (relationship between concentrations and pharmacologic effects or the time course of pharmacologic effects) and/or clinical outcome (in terms of efficacy and/or safety and tolerability). Some reported examples of PGx associations with safety/adverse events include:

Drug	Disease	Gene Variant	Outcome
Abacavir	HIV [Hetherington, 2002; Mallal, 2002; Mallal, 2008]	HLA-B*57:01 (Human Leukocyte Antigen B)	Carriage of the HLA-B*57:01 variant has been shown to increase a patient's risk for experiencing hypersensitivity to abacavir. Prospective HLA-B*57:01 screening and exclusion of HLA-B*57:01 positive patients from abacavir treatment significantly decreased the incidence of abacavir hypersensitivity. Treatment guidelines and abacavir product labeling in the United States and Europe now recommend (US) or require (EU) prospective HLA-B*57:01 screening prior to initiation of abacavir to reduce the incidence of abacavir hypersensitivity. HLA-B*57:01 screening should supplement but must never replace clinical risk management strategies for abacavir hypersensitivity.
Carbamazepine	Seizure, Bipolar disorders & Analgesia [Chung, 2010; Ferrell, 2008]	HLA-B*15:02	Independent studies indicated that patients of East Asian ancestry who carry HLA-B*15:02 are at higher risk of Stevens-Johnson Syndrome and toxic epidermal necrolysis. Regulators, including the US FDA and the Taiwanese TFDA, have updated the carbamazepine drug label to indicate that patients with ancestry in genetically at risk populations should be screened for the presence of HLA-B*15:02 prior to initiating treatment with carbamazepine.

Drug	Disease	Gene Variant	Outcome
Irinotecan	Cancer [Innocenti, 2004; Liu, 2008; Schulz, 2009]	UGT1A1 *28	Variations in the UGT1A1 gene can influence a patient's ability to break down irinotecan, which can lead to increased blood levels of the drug and a higher risk of side effects. A dose of irinotecan that is safe for one patient with a particular UGT1A1 gene variation might be too high for another patient without this variation, raising the risk of certain side-effects that include neutropenia following initiation of Irinotecan treatment. The irinotecan drug label indicates that individuals who have two copies of the UGT1A1 *28 variant are at increased risk of neutropenia. A genetic blood test is available that can detect variations in the gene.

A key component to successful PGx research is the collection of samples during the conduct of clinical studies.

Collection of whole blood samples or saliva samples, even when no *a priori* hypothesis has been identified, may enable PGx analysis to be conducted if at any time it appears that there is a potential unexpected or unexplained variation in response to orelizumab.

Pharmacogenetic Research Objectives

The objective of the PGx research (if there is a potential unexpected or unexplained variation) is to investigate a relationship between genetic factors and response to orelizumab. If at any time it appears there is potential variability in response in this clinical study or in a series of clinical studies with orelizumab, the following objectives may be investigated – the relationship between genetic variants and study treatment with respect to:

- Pharmacokinetics and/or pharmacodynamics of study treatment
- Safety and/or tolerability
- Efficacy

Study Population

Any subject who is enrolled in the clinical study, can participate in PGx research. Any subject who has received an allogeneic bone marrow transplant must be excluded from the PGx research.

Subject participation in the PGx research is voluntary and refusal to participate will not indicate withdrawal from the clinical study or result in any penalty or loss of benefits to which the subject would otherwise be entitled.

Study Assessments and Procedures

Saliva samples will be taken for Deoxyribonucleic acid (DNA) extraction and used in PGx assessments.

Saliva (2mL) is collected into the DNA self-collection kit. A single sample will be taken but can be duplicated if the first sample is unusable. It is recommended that the saliva sample be collected between Day 1 and 6.

- The PGx sample is labelled (or “coded”) with a study specific number that can be traced or linked back to the subject by the investigator or site staff. Coded samples do not carry personal identifiers (such as name or social security number). The saliva sample is taken on a single occasion unless a duplicate sample is required due to inability to utilize the original sample.

The DNA extracted from the saliva sample may be subjected to sample quality control analysis. This analysis will involve the genotyping of several genetic markers to confirm the integrity of individual samples. If inconsistencies are noted in the analysis, then those samples may be destroyed.

The need to conduct PGx analysis may be identified after a study (or a set of studies) of orelizumab has been completed and the clinical study data reviewed. In some cases, the samples may not be studied. e.g., no questions are raised about how people respond to orelizumab.

Samples will be stored securely and may be kept for up to 15 years after the last subject completes the study or GSK may destroy the samples sooner. GSK or those working with GSK (for example, other researchers) will use samples collected from the study for the purpose stated in this protocol and in the informed consent form.

Subjects can request their sample to be destroyed at any time.

Subject Withdrawal from Study

If a subject who has consented to participate in PGx research withdraws from the clinical study for any reason other than being lost to follow-up, the subject will be given a choice of one of the following options concerning the PGx sample, if already collected:

- Continue to participate in the PGx research with the PGx sample retained for analysis
- Withdraw from the PGx research and destroy the PGx sample

If a subject withdraws consent for PGx research or requests sample destruction for any reason, the investigator must complete the appropriate documentation to request sample destruction within the timeframe specified by GSK and maintain the documentation in the site study records. The investigator should forward the Pharmacogenetic Sample Destruction Request Form to GSK as directed on the form. This can be done at any time when a subject wishes to withdraw from the PGx research or have their sample destroyed whether during the study or during the retention period following close of the main study.

Screen and Baseline Failures

If a blood sample for PGx research has been collected and it is determined that the subject does not meet the entry criteria for participation in the clinical study, then the investigator should instruct the participant that their PGx sample will be destroyed. No forms are required to complete this process as it will be completed as part of the consent and sample reconciliation process. In this instance a sample destruction form will not be available to include in the site files.

Pharmacogenetics Analyses

Pharmacogenetics Analyses

Specific genes may be studied that encode the drug targets, or drug mechanism of action pathways, drug metabolizing enzymes, drug transporters or which may underpin adverse events, disease risk or drug response. These candidate genes may include a common set of ADME (Absorption, Distribution, Metabolism and Excretion) genes that are studied to determine the relationship between gene variants or treatment response and/or tolerance.

In addition, continuing research may identify other enzymes, transporters, proteins or receptors that may be involved in response to orelizumab. The genes that may code for these proteins may also be studied.

Genome-wide scans involving a large number of polymorphic markers (e.g., single nucleotide polymorphisms) at defined locations in the genome, often correlated with a candidate gene, may be studied to determine the relationship between genetic variants and treatment response or tolerance. This approach is often employed when a definitive candidate gene(s) does not exist and/or the potential genetic effects are not well understood.

If applicable and PGx research is conducted, appropriate statistical analysis methods will be used to evaluate pharmacogenetic data in the context of the other clinical data. Results of PGx investigations will be reported either as part of the main clinical study report or as a separate report. Endpoints of interest from all comparisons will be descriptively and/or graphically summarized as appropriate to the data. A detailed description of the analysis to be performed will be documented in the study reporting and analysis plan (RAP) or in a separate pharmacogenetics RAP, as appropriate.

Informed Consent

Subjects who do not wish to participate in the PGx research may still participate in the clinical study. PGx informed consent must be obtained prior to any saliva being taken for PGx research.

Provision of Study Results and Confidentiality of Subject's PGx Data

GSK may summarize the PGx research results in the clinical study report, or separately, or may publish the results in scientific journals.

GSK does not inform the investigator, subject, or anyone else (e.g., family members, study investigators, primary care physicians, insurers, or employers) of individual genotyping results that are not known to be relevant to the subject's medical care at the time of the study, unless required by law. This is due to the fact that the information generated from PGx studies is generally preliminary in nature, and therefore the significance and scientific validity of the results are undetermined.

References

12.3. Appendix 3: Country Specific Requirements

There are no country specific requirements.

12.4. Appendix 4: Procedures for Detection, Evaluation, Follow-Up and Reporting of Adverse Events

Recording of AEs and SAEs

When an AE/SAE occurs, it is the responsibility of the investigator to review all documentation (e.g., hospital progress notes, laboratory, and diagnostics reports) relative to the event. The investigator will then record all relevant information regarding an AE/SAE in the appropriate data collection tool.

It is not acceptable for the investigator to send photocopies of the patients' medical records to GSK in lieu of completion of the GSK, AE/SAE data collection tool. However, there may be instances when copies of medical records for certain cases are requested by GSK. In this instance, all patient identifiers, with the exception of the patient number, will be blinded on the copies of the medical records prior to submission of to GSK.

The investigator will attempt to establish a diagnosis of the event based on signs, symptoms, and/or other clinical information. In such cases, the diagnosis will be documented as the AE/SAE and not the individual signs/symptoms.

Evaluating AEs and SAEs

Assessment of Intensity

The investigator will make an assessment of intensity for each AE and SAE reported during the study and will assign it to one of the following categories:

Mild: An event that is easily tolerated by the patient, causing minimal discomfort and not interfering with everyday activities.

Moderate: An event that is sufficiently discomforting to interfere with normal everyday activities.

Severe: An event that prevents normal everyday activities.

An AE that is assessed as severe will not be confused with an SAE. Severity is a category utilized for rating the intensity of an event; and both AEs and SAEs can be assessed as severe. An event is defined as 'serious' when it meets at least one of the pre-defined outcomes as described in the definition of an SAE.

Assessment of Causality

The investigator is obligated to assess the relationship between study treatment and the occurrence of each AE/SAE. A "reasonable possibility" is meant to convey that there are facts/evidence or arguments to suggest a causal relationship, rather than a relationship cannot be ruled out. The investigator will use clinical judgment to determine the relationship. Alternative causes, such as natural history of the underlying diseases, concomitant therapy, other risk factors, and the temporal relationship of the event to the

study treatment will be considered and investigated. The investigator will also consult the Investigator Brochure (IB) and/or Product Information, for marketed products, in the determination of his/her assessment.

For each AE/SAE the investigator must document in the medical notes that he/she has reviewed the AE/SAE and has provided an assessment of causality.

There may be situations when an SAE has occurred and the investigator has minimal information to include in the initial report to GSK. However, **it is very important that the investigator always make an assessment of causality for every event prior to the initial transmission of the SAE data to the CRO Medical Monitor and GSK.** The investigator may change his/her opinion of causality in light of follow-up information, amending the SAE data collection tool accordingly. The causality assessment is one of the criteria used when determining regulatory reporting requirements.

Follow-up of AEs and SAEs

After the initial AE/SAE report, the investigator is required to proactively follow each patient at subsequent visits/contacts. All AEs and SAEs will be followed until resolution, until the condition stabilizes, until the event is otherwise explained, or until the patient is lost to follow-up.

The investigator is obligated to perform or arrange for the conduct of supplemental measurements and/or evaluations as may be indicated or as requested by GSK to elucidate as fully as possible the nature and/or causality of the AE or SAE. The investigator is obligated to assist. This may include additional laboratory tests or investigations, histopathological examinations or consultation with other health care professionals. If a subject dies during participation in the study or during a recognized follow-up period, the investigator will provide GSK with a copy of any post-mortem findings, including histopathology.

New or updated information will be recorded in the originally completed data collection tool. The investigator will submit any updated SAE data to GSK within the designated reporting time frames.

Reporting of SAEs to GSK

Electronic Facsimile and/or e-mail transmission of the paper SAE data collection form is the preferred method to transmit this information to the CRO and GSK Medical Monitors. In rare circumstances and in the absence of facsimile equipment, notification by telephone is acceptable, with a copy of the SAE data collection form sent by overnight mail. Initial notification via the telephone does not replace the need for the investigator to complete and sign the paper SAE data collection form within the designated reporting time frames.

CRO and GSK contacts for SAE receipt can be found at this beginning of the protocol on the Sponsor/Medical Monitor Contact Information page.

12.5. Appendix 5: Mixed Meal Tolerance Test (MMTT)

The Mixed Meal Stimulated C-peptide and C-peptide unstimulated will be performed as shown in the protocol Section 6.2 Time and Events Table

On the evening before the C-peptide analysis, subjects should eat a full, standard meal. They must fast from 12 PM the evening before the test until the test is completed. They should remain hydrated and may consume water, black coffee, or black tea (with no sugar or artificial sweeteners) during the fast and test.

Subjects will start the C-peptide analysis in the morning. The time at which the test is started should be kept as consistent as possible. Before the test is started, blood glucose will be measured using a finger-stick test. The Mixed Meal Stimulated C-peptide may be performed only if the blood glucose level is above **70 mg/dL** and no higher than **200 mg/dL**. Documentation that the glucose is in this range will be required. If the glucose is outside this range, this test must be rescheduled.

On the morning of the test, subjects will modify their insulin regimen as follows:

- For subjects who do not use an insulin pump: withhold the morning dose of long- or intermediate-acting insulin. No regular insulin for at least 6 hours before the test; no very short-acting insulin for at least 2 hours before the test.
- For subjects who use an insulin pump: continue the basal insulin rate until the start of the test, then stop the pump. No regular insulin boluses for at least 6 hours before the test; no short-acting insulin boluses for at least 2 hours before the test.

When both unstimulated and Mixed Meal stimulated C-peptide analysis should be done, each subject will consume a standardized amount of Ensure Powder (Abbott) drink supplied by the CRO/GSK. Further details on this product are provided in the study reference manual.

The time when the subject starts drinking the Ensure will be defined as Time 0. The subject will drink the Ensure powder solution within 5 minutes or less. Blood samples will be taken 10 minutes before and immediately before the subject starts drinking the Ensure drink at Time 0. These 2 blood samplings belong to the unstimulated C-peptide analysis. For the Mixed Meal stimulated C-peptide analysis, blood sampling will be done at 15, 30, 60, 90, and 120 minutes after Time 0. The subject may consume water or unsweetened black coffee or tea during this period.

If only the unstimulated C-peptide analysis should be performed (Protocol Section 6.2 Time and Events Table), 1 blood sample is sufficient.

A snack appropriate for a subject with diabetes will be available immediately after the 120-minute blood draw. Glucose will be measured by finger stick; insulin and/or a snack will be given as indicated. As soon as feasible after completing the C-peptide analysis test, subjects will resume their usual insulin and diet regimens.

The tubes with the blood samples will be kept on ice during collection, until centrifuged for 15 min at 1530 x g and 4°C. The plasma will be harvested into 2 green cap transfer vials 2.0 mL and stored at <-15°C until shipment (within 3 weeks of collection). The tubes must be shipped on dry ice and remain frozen until analysis. Further details will be provided in the SRM.

12.6. Appendix 6: Hyperglycaemic Clamp Procedure

1. The evening before the clamp procedure:

AIM: Keep blood glucose (BG) between 80-120mg/dl

- 8pm+: Sc long acting insulin (if basal-bolus therapy) or sc rapid insulin (if sc insulin pump) are replaced by intravenous Actrapid with pump. Blood Glucose measurements every 2h and adapt Actrapid IV treatment as described in the SOP of the hospital, with aim of BG \approx 90mg/dL at 8am on day of clamp, and without episodes of hypoglycaemia during the night before.

2. Day of clamp procedure:

A. Euglycemic Phase:

AIM: Keep blood glucose between 60-90mg/dl during 180 minutes.

Start Euglycemic phase only when BG 60-90mg/dL

Measure blood glucose every 15 minutes and adapt according to [Table A](#)

Table A:

Blood Glucose (BG)	Actrapid HM Pump IV	Infusion 100ml/hr
Start = t0		
80-90 mg/dL	Daily dose/24/hr	NaCl 0.9%
50-80 mg/dL	0.5IU/hr	NaCl 0.9%
<50mg/dL	STOP TEST*	Glucose 5%
Adaptation of insulin pump during test:		
Adapt Actrapid IV if BG >60mg/dL		
Increase >10mg/dL	+0.5IU/hr	NaCl 0.9%
Decrease >10mg/dL	- 0.5 IU/h	NaCl 0.9%

Blood Glucose (BG)	Actrapid HM Pump IV	Infusion 100ml/hr
Adapt Actrapid IV if BG 50 - 60mg/dL		
	0.5IU/h	NaCl 0.9%
Never stop insulin Pump during the test unless BG <50mg/dL = STOP TEST*		

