6. STUDY ASSESSMENTS AND PROCEDURES

This section lists the procedures and parameters of each planned study assessment. The exact timing of each assessment is listed in the Time and Events Table Section 6.2. Whenever vital signs, 12-lead ECGs and blood draws are scheduled for the same nominal time, the assessments should occur in the following order: PK, safety blood samples, ECG, vital signs, and PD samples.

Protocol waivers or exemptions are not allowed with the exception of immediate safety concerns. Therefore, adherence to the study design requirements, including those specified in the Time and Events Table, are essential and required for study conduct.

The timing and number of planned study assessments, including: safety, pharmacokinetic, pharmacodynamic, biomarker or other assessments may be altered during the course of the study based on newly available data (e.g. to obtain data closer to the time of peak plasma concentrations) to ensure appropriate monitoring. The change in timing or addition of time points for any planned study assessments must be approved and documented by GSK, but this will not constitute a protocol amendment. The IRB/IEC will be informed of any safety issues that require alteration of the safety monitoring scheme.

No more than approximately 500 mL of blood will be collected over the first 3 month period, including any extra assessments that may be required. The volume of blood collected after the first 3 months will be lower, eg less than 200 mL.

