6.7.2. Hyperglycaemic Clamp Serum Stimulated C-Peptide Levels and C-Peptide AUC

Plasma C-peptide and glucose levels will be measured during the hyperglycaemic clamp procedure at the following time points: L150, L165 and L180 minutes [during the euglycaemic (L)ow phase], H0, H60, H90, H120 and H140 minutes [during the hyperglycaemic (H)igh phase]. C-peptide AUC will be the area under the C-peptide/time curve from Time H60 to H140 minutes (Figure 6). AUC will be expressed as value per minute for each period. This value will be calculated at baseline, 6 and 24 months.

Figure 6 Schematic showing the Euglycaemic and Hyperglycaemic phases of the Clamp Procedure

See [Appendix 6](#) for the procedure that must be followed for the hyperglycaemic clamp test.

NB. The MMTT and hyperglycemic clamp test must be separated by at least 4 days

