9.2. Sample Size Considerations

9.2.1. Sample Size Assumptions

There are no formal calculations of power or sample size for this study. The sample sizes have been chosen based on feasibility, to primarily allow characterization of safety and tolerability of ascending doses of otelexizumab, in T1DM patients.

A total of 40 patients will be recruited into the study and for each cohort, 8 patients will be randomized to otelexizumab and 2 patients to placebo.

The primary objective of the study is based on safety and tolerability, where safety events are of interest, particularly those related to CRS and EBV reactivation which have associated defined stopping criteria. From a expected benefit : risk perspective it would be unacceptable to continue dosing patients within a cohort or subsequent cohorts, if ≥ 3 subjects met the defined CRS or EBV stopping criteria described in Section 5.3 Patient Specific and Dose Escalation Stopping Criteria.

Assuming we were to observe a number of events out of the 8, then in Table 10, the following are estimated for various numbers of observed responders:

- [1] 95% credible intervals for proportion of responders
- [2] Probability of response rate >0.375 , derived within a Bayesian framework with a non informative conjugate prior distribution, Beta (1, 1), for the response rate.

Table 10 Estimated 95% Credible Intervals for Proportion of Responders & Probability of Response Rate >0.375

Total No. of Subjects Per Cohort	Observed No. of Responders	95% Credible Interval for Proportion of Responders, Given Observed Data	Probability of Response Rate >0.375 (3/8), Given Observed Data
8	0	(0.00 , 0.34)	0.01
8	1	(0.03 , 0.48)	0.09
8	2	(0.07 , 0.60)	0.28
8	3	(0.14 , 0.70)	0.55
8	4	(0.21 , 0.79)	0.78
8	5	(0.30 , 0.86)	0.93
8	6	(0.40 , 0.93)	0.98
8	7	(0.52 , 0.97)	0.99
8	8	(0.66 , 1.00)	1.00

If we were to observe 0 out of 8 subjects with a given CRS or EBV event, the estimated 95% credible interval for the proportion of responders is (0.00, 0.34) and there would be a very low probability (0.01) of the true response rate being greater than 0.375.

However, if we were to observe 3 out of 8 subjects with a given CRS or EBV event, the estimated 95% credible interval for the proportion of responders is (0.14, 0.70) and there would be a 0.55 probability of the true response rate being greater than 0.375.

In the above scenario where 3 out of 8 subjects have a given CRS or EBV event:

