***: Stop test + REPEAT Clamp 1 day later**

Take blood samples for C-Peptide (Trasylol-EDTA on ice) and glycaemia (NaF) at:

Time	Sample Name
Time 0 + 150 min	L150
Time 0 + 165 min	L165
Time 0 + 180 min**	L180

B. Let blood glucose increase till 180mg/dL

AIM: increase BG till 180mg/dL in a period of 30 minutes.

At Time 0 + 180 min**: **STOP Actrapid IV** and **START glucose 10%** at 50 mL/hr during 15 minutes.

Measure blood glucose every 15 minutes and adapt according to [Table B](#). Blood glucose should increase to minimally 180 mg/dL with help of glucose infusion.

Table B:

	Blood Glucose (BG)	Actrapid HM Pump IV	Glucose Infusion
Adaptation of glucose infusion till BG 180mg/dl:			
15'	<180 mg/dL	STOP	Increase Glucose 10% to 100ml/h
15'	<180 mg/dL	STOP	Replace Glucose 10% by Glucose 20% at 100ml/h (same rate)
15'	<180 mg/dL	STOP	Keep Glucose 20% infusion at 100ml/h (same rate)
180-240mg/dL: START Test =Time 0***			

C. Hyperglycemic Phase start BG 180-240mg/dL

AIM: keep hyperglycaemia (range 180-240mg/dL) during 140 minutes.

When blood glucose >180 mg/dL = Time 0***

Take blood samples for C-Peptide (Trasylol-EDTA on ice) and glycemia (NaF) at:

Time	Sample Name
Time 0***	H0
Time 0 + 60 min	H60
Time 0 + 90 min	H90
Time 0 + 120 min	H120
Time 0 + 140 min	H140

Measure BG at least every 15 min and adapt according to [Table C](#).

Table C:

	Blood Glucose (BG)	Actrapid HM Pump IV	Infusion
	180-240mg/dL	STOP	Keep glucose infusion
Adaptation of glucose infusion if BG >240mg/dl:			
15'	>240 mg/dL	STOP	Glucose 10% 100ml/h
15'	>240 mg/dL	STOP	Glucose 10% 50ml/h
15'	>240 mg/dL	STOP	NaCl 0.9% 50ml/h
Adaptation of glucose infusion if BG <200mg/dl:			
15'	<200 mg/dL	STOP	Glucose 10% 50ml/h
15'	<200 mg/dL	STOP	Glucose 10% 100ml/h
15'	<200 mg/dL	STOP	Glucose 20% 100ml/h

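### Clamp Table A: at low rates the -0.5 IU/h step can compute to zero against the no-stop rule, and the fixed 0.5 IU/h at 50-60 mg/dL can raise insulin as glucose falls (minor)

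*Protocol*

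**What the plan says.** Protocol Section 6.7.2 refers to Appendix 6 "for the procedure that must be followed for the hyperglycaemic clamp test". The euglycaemic phase has a target of 60-90 mg/dL for 180 minutes and an entry rule: "Start Euglycemic phase only when BG 60-90mg/dL". During it, staff are told: "Measure blood glucose every 15 minutes and adapt according to" Table A. The table contains:

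- **Start rate.** At 80-90 mg/dL, the patient's daily dose divided by 24, per hour. At 50-80 mg/dL, 0.5 IU/h.
- **Above 60 mg/dL.** A rise of more than 10 mg/dL adds 0.5 IU/h, and a fall of more than 10 mg/dL subtracts 0.5 IU/h. No minimum rate is given.
- **At 50-60 mg/dL.** Under "Adapt Actrapid IV if BG 50 - 60mg/dL" the rate is 0.5 IU/h, whatever it was before.
- **Last row.** "Never stop insulin Pump during the test unless BG <50mg/dL". Below 50 the test is stopped and the clamp is repeated a day later.

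The hospital's own procedure is invoked only for the evening before the clamp. Neither the protocol nor the SAP states a minimum rate or a rule against increasing insulin at 50-60 mg/dL.

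**The concern.** Three rows interact badly once the rate is low. The reduction step can take the computed rate to zero or below while glucose is still above 60, where the last row bars stopping the pump. The 50-60 row can then lift a rate that earlier reductions had brought below 0.5 IU/h, and it does so when glucose has just dropped under the target range and is approaching the stop threshold. In the first case no rate satisfies both rows. In the second the written rule moves insulin in the opposite direction from the preceding reductions. This is a mandatory insulin-dosing instruction in a multi-centre study, and sites that fill the gap themselves may fill it differently.

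**Working it through.** The documents give no figure to reproduce, so the check applies Table A literally, comparing each reading with the one 15 minutes before.

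**Inputs.** The start rates, steps and thresholds are as in Table A. The daily dose D is an assumption, because the documents give no patient doses. Rates are in IU/h and glucose in mg/dL. A reading of exactly 60 falls in the 50-60 row, and a change of exactly 10 triggers no step.

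| Start | Readings | Computed rate | Result |
|---|---|---|---|
| 0.5 row (no dose needed) | 75, 63 | 0.5, 0 | zero above 60 |
| D = 24 | 90, 79, 68 | 1.0, 0.5, 0 | zero above 60 |
| D = 18 | 90, 79, 68 | 0.75, 0.25, -0.25 | negative above 60 |
| D = 30 | 90, 79, 68, 57 | 1.25, 0.75, 0.25, 0.5 | rises on falling glucose |
| D = 40, with rebound | 90, 79, 89, 78, 67, 60 | 1.67, 1.17, 1.17, 0.67, 0.17, 0.5 | rises on falling glucose |
| D = 60, with recovery | 90, 80, 70, 60, 68, 76, 65 | 2.5, 2.5, 2.5, 0.5, 0.5, 0.5, 0 | zero above 60 |
| D = 30, slow fall | 90, 80, 70, 60 | 1.25, 1.25, 1.25, 0.5 | reduced, as intended |

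**When a zero rate can arise.** From the 0.5 IU/h start row, one fall of at least 11 that ends above 60 is enough: 0.5 - 0.5 = 0. In whole mg/dL this is possible for starts at 72-80, since 72 - 11 = 61. From starts at 83-90, two such falls fit (83 - 22 = 61), and D/24 - 1.0 is zero or less when D is 24 or less.

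**When a rise can arise on a steady fall from 80-90.** At most two reductions fit before the 50-60 band, so the rate on entry is at least D/24 - 1.0. This is below 0.5 only if D/24 < 1.5, that is D < 36 IU/day. The 40 IU/day row shows that 36 is not a general upper limit, because a rebound leaves room for a third reduction.

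**Size of the excess until the next reading (0.25 h).**

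- D = 30: (0.5 - 0.25) x 0.25 = 0.0625 IU.
- D = 40: (0.5 - 0.167) x 0.25 = 0.083 IU.
- Ceiling, with the pump at zero beforehand: 0.5 x 0.25 = 0.125 IU.

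**Reach into the endpoints.** At the end of the 180 minutes Appendix 6 part B says "STOP Actrapid IV", before any high-phase sample is drawn. The clamp AUC uses H60-H140. The insulin sensitivity index in SAP 11.5.4 uses 120-140 minutes of the hyperglycaemic phase. The only derived quantity in the SAP that uses low-phase clamp samples is a HOMA calculation, and that is optional.

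**The case against.** The strongest reply is that the table, read as a whole, already answers the point. Its only fixed running rate is 0.5 IU/h, which appears in both the 50-80 start row and the 50-60 row. Together with the ban on stopping the pump, this suggests 0.5 IU/h as a running minimum. That reading is sensible and removes the zero and the rise in the worked sequences. It is not written, however, in Table A or elsewhere in the protocol or SAP. The no-stop row excludes zero without saying what rate to use instead. The study reference manual is not available and might give one, but Appendix 6 does not refer to it.

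A second reply is that the sequences are constructed. Doses are assumed, and the 30 IU/day example needs three successive falls of 11 mg/dL in spite of falling insulin. This stands as a limit on frequency, which the documents cannot settle. The 75-then-63 case, though, needs no assumed dose and a single fall of 12.

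A third reply is that the consequence is small. This stands in full: the excess is bounded, glucose is rechecked every 15 minutes, and a reading below 50 ends the test. Nor are staff bound to a rate they think unsafe, since Section 6 says "Protocol waivers or exemptions are not allowed with the exception of immediate safety concerns".

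A reader might also infer that the table leaves open which reading the 10 mg/dL change is measured from. With checks every 15 minutes, the previous reading is the obvious comparator.

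**Conclusion.** The inconsistency is real but minor. Applied literally, a mandatory dosing table can give a rate that its own last row forbids, and can raise insulin as glucose falls into 50-60 mg/dL. The excess cannot exceed 0.125 IU per 15-minute interval. The zero-rate case rests on the table alone. The rise after a start at 80-90 mg/dL rests on assumed daily doses, and on a steady fall it needs less than 36 IU/day. Patients who enter the 50-60 band above 0.5 IU/h are correctly reduced.

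Two stronger inferences are not supported. One is that the clamp C-peptide results are biased: insulin is off before the high-phase samples, and no effect on a planned endpoint is shown. The other is that patients face a material or frequent risk of hypoglycaemia: no doses or frequencies are given, and the recheck and stop rules limit exposure.

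**What to change.** Make two edits to Table A. In the 50-60 mg/dL row, set the rate to the lower of 0.5 IU/h and the current rate, and say that it is not to be increased. For the 0.5 IU/h reduction, state an explicit non-zero minimum that never raises a rate already below it.

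The minimum is a clinical choice for the sponsor's team, and the documents point to no value. Its consequences differ. With an illustrative 0.1 IU/h, readings of 75, 63, 57 give 0.5, 0.1, 0.1, and 30 IU/day on 90, 79, 68, 57 gives 1.25, 0.75, 0.25, 0.25. With 0.5 IU/h the second sequence gives 1.25, 0.75, 0.5, 0.5, which is more insulin at 68 mg/dL than the present table gives. The slow fall at 30 IU/day is unchanged under either value.

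The cost is a few lines in one appendix, with no new data or visits. The drawback is comparability. Clamps are planned at Day -1, Month 6 and Month 24, and SAP Section 2.3 reports that escalation stopping criteria were met in Cohort 3, so baseline clamps are probably complete. Later clamps that reach low rates would then follow slightly different insulin rules from the baseline they are compared with. Tests that never reach a low rate would run as before, and the wording would also serve any reuse of the procedure.
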